## Baseline Appointments

**We are looking to get an accurate reading of CO levels. Therefore, be sure to schedule these appointments during late morning or early afternoon.**

**Administration time: Approximately 150 minutes**

**Do not schedule any appointments until 2.5 hours after the start of your baseline appointment.**

## Materials

- CO Machine and new white mini mouthpiece
- Urine cup

- Urine lid and gloves
- Pregnancy test (if participant is female)
- Cotinine test
- Surface Pro
- Two Consent forms
- Contact sheet
- Screening form
- Greenphire ClinCard

## Procedures

1. Go through the Consent Form with the participant, addressing any questions or concerns they may have.
2. Have the participant sign and date where it states “Signature of Participant” on page 6 of the Consent Form. Make sure that they also sign on page 7 (Authorization for Use/Disclosure of Personal Health Information (PHI) for Research), on which they need to print their name at the top of the page and sign/date at the bottom of the page where it says “Signature of Participant.”
3. Be sure that you also sign the consent form on page 6 as the “Person Obtaining Consent.”
4. The participant will receive one signed copy of the consent, and we will keep one signed copy for our records.
5. Administer the CO test. Refer to the CO directions under the “Carbon Monoxide Monitor” section on page 8 of this manual.
6. Place a lid on urine cup and take the participant to the restroom for the urine screen.
7. After the participant uses the restroom, have them hand you the cup so that you can administer the pregnancy test (for women only) and the cotinine test. After these tests, you should discard the urine sample and all tests and head back to the office.
8. Have the participant complete the contact sheet.
9. Set up the participant in the Pre-Randomization arm.
10. Once the Pre-Randomization is completed, complete the last form remaining in REDCap, “Group Assignment,” to randomize the participant into one of the groups.
11. Once the participant is randomized into a group, have the participant fill out the Baseline questionnaires for that group on the tablet or on the computer in an office. Do not allow them to fill out in waiting room or any other office where we are not present.
12. Monitor the participant’s progress in REDCap.
13. Schedule the first intervention session for the following week, at least 5 days from Baseline. Also, it is important for participants in the Intervention groups to be scheduled for their weekly appointment in the morning. Once you have it scheduled, make sure the appointment is placed on your UABMC calendar and google calendar (MOP, pg. 14).
14. Instructions for participants for Session 1 are as below, according to which group they have been assigned:
  - If the participant is in an **Intervention** group then say, “**When you come in for your appointment on \_\_\_\_\_ at \_\_\_\_\_ please refrain from smoking the night before your appointment, and the morning of.**”
  - If the participant is in the **Control** group, there are no special instructions for the next appointment.

15. Complete the \$10.00 ClinCard payment.
16. Give the participant an appointment card. That completes the Baseline appointment!

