### Random Assignment:

Complete the Data Entry Process as instructed under **Entering New Participant**. One of the forms under the REDCap documents for the Baseline Visit (BL) is titled **Group Assignment**. Once in this form, click the randomize button on this document to randomly assign the participant.

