### **Survey Queue:**

The survey queue is a way for participants to fill out questionnaires in REDCap in a more user-friendly display. When in survey mode, the screen simply shows the questionnaire with a submit button at the bottom. Once begun, the questionnaires will automatically load in the appropriate order corresponding to whichever session or visit the participant is attending. If a subject accidentally forgets to answer something, the survey prevents them from moving on, which gives staff the opportunity to assist if necessary. It is very important to note that surveys must be completed in the order they are shown.

To access the survey queue:

- Follow the steps as above, titled “Entering New Participant Data” or “Adding to Existing Participant Data”, depending on whether you are working with a new or existing subject
- From the **Record Home Page**, select the **CO Level** Data Collection Instrument, corresponding to the appropriate appointment, e.g. Baseline, Week 1, etc.
- Toward the upper right corner of the form, there is a gray drop down box titled **“Survey Options.”** Click this box and select **“Open Survey.”** A new tab will open displaying the form now in survey display. If the tab does not open, try clicking **“Open Survey”** again or double-clicking.
- Staff should fill out **CO Level**, select **“Submit”**, and the next form will auto load. The survey queue is set up to stop before loading the questionnaires for participants. The screen will indicate you have finished with that set of surveys, and will provide a link at the bottom to start the next set to be filled out by the participant.

- When appropriate, select that link and have the participant proceed through the queue. The queue will automatically stop again before loading any other questionnaires intended to be filled out after the counseling session or completed by staff, for example.

\*\*You can access the survey queue from any of the measures set up as surveys by again selecting “**Open Survey**” from the gray “**Survey Queue**” drop down box toward the upper right corner of the page.

\*\*Surveys display on the **Record Home Page** as complete with a green circle and white check mark.

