
C. Approach

Design and Overview. This pilot study will examine the feasibility, acceptability, and preliminary impact of providing an In vivo intervention with NRT to increase NRT adherence compared to the control group. The intervention will be tested and refined initially with 10 participants in the In vivo NRT group (In vivo). Following the pre-pilot testing, 80 participants will be randomized to either the 1) In vivo or 2) Standard of Care (SC). All participants will complete approximately 60 minutes of baseline assessment to determine smoking history and characteristics prior to randomization, including previous experience with NRT. In vivo participants will be provided with each of the four forms of acute NRT (gum, lozenge, nasal spray, inhaler per week; counterbalanced across sessions by participant) to use in each 30 minute session in conjunction with a nicotine patch. In session, they will discuss their In vivo experience of using each combination NRT at each of the four sessions. To bolster their in vivo NRT experience, participants will be provided with a weekly sample of each NRT product to use between sessions to acclimate to the medication and to make PQAs. After the 4 week In vivo intervention period, participants will select their preferred acute NRT product to use with the nicotine patch (combination NRT; cNRT) to use for cessation over the next eight weeks. SC participants will receive four sessions of standard behavioral smoking cessation counseling and will select their preferred acute NRT (gum, lozenge, nasal spray, inhaler) based on product description. Thus, both groups will receive cNRT for 8 weeks total to make a quit attempt. All participants will continue to receive medication and monitoring for side effects, regardless of their medication adherence. Study visits occur at baseline (Week 0), intervention Weeks 1-4, medication selection/quit goal setting visit at Week 5, medication check (Week 6) Weeks 9 and 13 (end-of-treatment), and follow-up at one month later (Week 17; see Figure 1 for Study Design).

[figure not shown]
Preliminary Studies. The PI and her team have completed studies directly relevant to the current proposal and have worked with several different low income and disadvantaged populations such as individuals in the criminal justice system and Persons Living with HIV (PLWH).

Figure 1: Proposed Study Design from Recruitment to One Month Follow-up

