Combination Nicotine Replacement (cNRT). Participants will be screened at the time of their baseline appointment for the appropriateness of all NRT products. Our physician collaborator will be available to answer any questions that may arise when screening participants and will assist the PI in evaluating any adverse events believed to be related to the use of NRT. All participants will be evaluated for their initial NRT dose based on Federal Drug Administration guidelines. Participants who smoke 10 or fewer cpd will start at 14mg patch while smokers who use 11 or more cpd will start at 21mg patch. The nicotine inhaler delivers 4 mg of nicotine per cartridge (inhaling for 20 minutes on each cartridge) with participants using about 6 cartridges daily. Nicotine nasal spray delivers 0.5mg of nicotine per spray with one spray per nostril (1mg total) recommended 1-2 times per hour. Participants will be given the 2mg nicotine gum or lozenge to use. The safety and tolerability of using NRT products together or smoking while using NRT has been demonstrated^{e.g.51}. Further, the rationale for using combination NRT over a single agent is two-fold. First combination NRT has demonstrated the best efficacy for promoting abstinence over all other single agents with the exception of varenicline⁵⁸. Second, NRT is short-acting and can be administered in-session to demonstrate the effect of this medication in relieving withdrawal symptoms, including craving. NRT can also be used sporadically as is proposed during the sampling weeks. Other smoking cessation pharmacotherapies (e.g., bupropion, varenicline) take about a week to titrate to full effect²⁶. Both groups will receive 8 weeks of medication for a sustained quit attempt, although the In vivo group will be sampling four different short acting NRT products during the first four weeks of the intervention.

Baseline and Assessment Measures. After eligibility determination and consent to participate, the baseline assessment will be administered. This assessment is expected to take about 60 minutes and will provide basic smoking history, smoking behavior, and proposed mediators and moderators such as treatment interest, expectancies for NRT, previous use of NRT, craving, withdrawal, and side effects associated with NRT use (see Table 1 description) and will be repeated during the study period (see Table 2 for assessment schedule).

Table 1: Instrument Description

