NRT Adherence	X	X	X	X	X	X	X	X	X	

Note: BL=Baseline Assessment; S=session; WK=week; M=month; PS=Product Selection; ¹All participants will complete these surveys twice (at the beginning and end of session) during sessions 1-4.

Randomization. We anticipate enrolling 10 pre-pilot participants in 3 months and 80 participants in 20 months and, based on our previous study with this population, expect to retain at least 70% through the one month follow-up point. Randomization will occur after completion of the initial screening and assessment.

Primary Outcomes. Feasibility and acceptability will be measured through high study retention (70%) and recruitment (recruitment of all participants within 24 months) in our groups. Additional items of acceptability include high scores on treatment satisfaction and credibility/expectancies that are equal or higher to the SC

group. Medication adherence is a third primary outcome with expected differences between our groups. Adherence is notoriously difficult to determine. Self-reported adherence is not always reliable, particularly during treatment studies where there is a demand characteristic to report the desired targeted behavior⁷³⁻⁷⁴ (e.g., adherence to NRT). The behavioral methods described under the assessment section represent the best available self-report tools for determining NRT adherence (e.g., TLFB report, returning used NRT patches and used product blister packs/packaging). Adherence will be defined by self-report using the TLFB and verified through returned patches and packaging. Good adherence is defined by taking greater than 80% of doses of medication at each time point. We have used these techniques in previous studies with low income populations with good compliance for use of TLFB verified by return of NRT materials⁷⁵.

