To test Aim 3, we will examine medication adherence during the 8 week intervention period between the intervention groups using Chi Square analyses at weeks 6, 9 and 13. Medication adherence will be defined as a self-reported use of taking 80% of medication as prescribed at each time point for both groups (adherent or not adherent). We can also look at adherence as a continuous proportion variable: adherence = number of doses taken / the number of doses given. We will also examine demographic and smoking characteristics (particularly withdrawal, cravings, abstinence self-efficacy, and NRT perceptions) that would be associated with medication adherence at weeks 6, 9 and 13 using logistic regression. These analyses will allow us to examine important associations with medication adherence in these groups.

To examine underlying factors believed to be important for medication adherence, particularly withdrawal, craving, self-efficacy, and perceptions of NRT, we will also examine these factors by intervention groups across time using paired t-tests, as appropriate. We are primarily interested in determining if our In vivo group had decreases in withdrawal and cravings, while increasing abstinence self-efficacy and NRT perceptions relative to the SC group. Given the pilot nature of this intervention, we will be able to examine 24-hour quit attempts and abstinence, but these factors are not the main focus on analyses as we will likely be underpowered to find significant differences on these outcomes with this small of a sample. While 80 participants may seem like a fairly large sample for a pilot study, a sample size between 500-600 participants is typical for most smoking cessation interventions and would be needed to examine important moderators and mediators of cessation. However, we will be able to obtain initial effect sizes that will be useful for determining the appropriate sample size for a fully-scaled R01 project in the future, if this intervention appears promising.

Missing data. There is a high likelihood that we will have participants who may miss an appointment, do not complete the study, or are otherwise lost to follow-up. Because of the potential of bias due to non-missing

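### The baseline procedure has participants complete the Baseline questionnaires after randomisation, against the SAP and the protocol's own form order, so the self-report baselines may be post-randomisation measures

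*Protocol*

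**What the plan says.** **Protocol, Baseline Appointments, Procedures.** Steps 1 to 9 cover consent, the CO test, the urine tests, the contact sheet and setting the participant up in the Pre-Randomization arm. Step 10 randomises: "Once the Pre-Randomization is completed, complete the last form remaining in REDCap", that form being *Group Assignment*. Step 11 follows: "Once the participant is randomized into a group, have the participant fill out the Baseline questionnaires for that group on the tablet". It also requires staff to be present while the forms are completed. Group-specific instructions to the participant come only at step 14.

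**SAP, Design and Overview:** "All participants will complete approximately 60 minutes of baseline assessment to determine smoking history and characteristics prior to randomization". **SAP, Randomization:** "Randomization will occur after completion of the initial screening and assessment". The assessment schedule in SAP Table 2 likewise separates the baseline column from a block headed as post-randomisation.

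**SAP, Baseline and Assessment Measures** describes what that assessment holds: it "will provide basic smoking history, smoking behavior, and proposed mediators and moderators such as treatment interest, expectancies for NRT", along with craving and withdrawal.

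**Elsewhere in the protocol,** the Random Assignment instruction opens "Complete the Data Entry Process as instructed under" the section on entering a new participant, and only then sends staff to the randomise button. The Measurement Occurrence Chart and the Data Collection Parameters list *Group Assignment* below all, or nearly all, of the Baseline questionnaires. The Survey Queue section adds: "It is very important to note that surveys must be completed in the order they are shown".

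**SAP, Data Management and Statistical Analysis (Aim 3),** on withdrawal, craving, self-efficacy and NRT perceptions: "we will also examine these factors by intervention groups across time using paired t-tests, as appropriate". The stated interest is in change in the In vivo group relative to standard of care.

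**The concern.** A baseline used to judge change between randomised arms should be one that the assignment could not have influenced. Step 11 removes that guarantee for every self-report form: Treatment Expectations, ANRT-12, the TAA self-efficacy item, SAQ, ARME, QSU and MNWS. The arms cannot be masked. One samples NRT from Week 1, and the other receives counselling with no medication until Week 5. A participant who learns this before rating expected benefit, confidence or attitudes to NRT may answer differently, in a direction that cannot be predicted.

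At stake are the comparisons of these measures by group across time, and any use of their baseline values as predictors in the adherence logistic regressions. The SAP gives the mechanism question as a reason for running the pilot before a larger trial.

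There is also a consistency problem. No passage says which forms sit in the Pre-Randomization arm. Staff can find support in the manual for either order, so the order may differ between participants.

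**Working it through.** **1. Does the SAP's baseline assessment mean the questionnaires?** It could be read as only the CO and urine tests, which the protocol does place before randomisation. Adding the Table 1 minutes for instruments marked at baseline in Table 2:

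- Pre-consent screener: 3
- Urine drug screen and CO: 1 + 1 = 2
- Self-report forms: demographics 1, smoking history 10, treatment expectancies 5, PSS 1, TAA 1, SAQ 5, ARME 5, ANRT-12 5, FTND 5, WISDM 10, QSU 5, MNWS 5, side effects 5, NRT adherence 5 = 68
- Total: 3 + 2 + 68 = 73

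The SAP allows about 60 minutes before randomisation. Two minutes of testing cannot fill that, so the assessment has to be the questionnaire battery, which is what step 11 places afterwards.

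**2. The order in each place**

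| Source | Order |
|---|---|
| SAP, Design and Overview | Assessment, then randomisation |
| SAP, Randomization | Assessment, then randomisation |
| Protocol, step 10 | *Group Assignment* is the last form left |
| Protocol, Measurement Occurrence Chart with the Survey Queue rule | *Group Assignment* is marked as a survey and listed below the Baseline questionnaires |
| Protocol, Random Assignment | Data entry, then randomise (extent of data entry not spelled out) |
| Protocol, step 11 | Randomisation, then questionnaires |

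Step 11 stands alone.

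**3. Illustration of size.** The documents give no disclosure effect, no allocation ratio and no correlation, and there is no plan figure to reproduce. Inputs:

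- From the SAP: 80 randomised, 70% retained.
- Assumed: 1:1 allocation; baseline/follow-up correlation r of 0.3, 0.5 or 0.7; a baseline shift of 0.1, 0.2 or 0.3 SD in one arm only; no true effect; a two-sample t-test on change from Baseline.

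Retained per arm: 40 × 0.70 = 28. In units of the SD of a single measurement, the SD of change is √(2(1 − r)) and the standard error of the between-arm contrast is that × √(2/28). The bias equals the shift, with opposite sign. The rejection rate is from the noncentral t, 54 df, two-sided 5%, noncentrality = shift/SE.

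| r | SD of change | SE | Shift 0.1 | Shift 0.2 | Shift 0.3 |
|---|---|---|---|---|---|
| 0.3 | 1.18 | 0.316 | 6.1% | 9.5% | 15.4% |
| 0.5 | 1.00 | 0.267 | 6.6% | 11.4% | 19.7% |
| 0.7 | 0.77 | 0.207 | 7.6% | 15.8% | 29.6% |

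At r = 0.5 the bias is 0.1/0.267 = 0.37, 0.2/0.267 = 0.75 or 0.3/0.267 = 1.12 standard errors.

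**4. Follow-up values only.** The standard error is √(2/28) = 0.267 at any r, with no bias from a shifted baseline. Against the change score this is equal at r = 0.5, smaller at 0.3 (0.267 against 0.316) and about 29% larger at 0.7 (0.267/0.207 = 1.29).

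**The case against.** The strongest reply is that no bias is documented. Nothing in the procedures tells participants their group before step 14, which comes after the questionnaires, and they answer the forms themselves in survey mode. This stands as a limit: without disclosure, bias through participant knowledge is zero. But nothing forbids earlier disclosure, and staff present during completion belong to a team that has just run the randomisation.

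Second, the rejection rates model a test the SAP does not specify. It names paired t-tests by group, does not name the Baseline visit as reference, and gives no allocation ratio, while the protocol describes four intervention groups plus control. This also stands: the figures are illustrative. The SAP does, however, state its question as change relative to standard of care, and all four factors are measured at Baseline.

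Third, withdrawal and craving are also measured before and after each session. If those within-session changes are what the paired tests use, the exposure narrows to self-efficacy and NRT perceptions.

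Fourth, the SAP calls the measures proposed mediators and moderators but sets out no mediation or moderation model, and says 500-600 participants would be needed to examine moderators and mediators of cessation. The argument from those roles is therefore the weaker one.

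Fifth, some of the protocol evidence is soft. The occurrence chart shows timing by visit, and it also lists *Group Assignment* after the two Alliance Questionnaires, which are given only at Week 5. The Random Assignment section points to steps that end by opening the CO form, so it adds little. The firm conflicts are step 11 against step 10 and step 11 against the SAP, and these are enough.

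**Conclusion.** The concern holds. Step 11 contradicts two statements in the SAP and the step before it. If followed as written, it makes the self-report baselines post-randomisation measures. This should be fixed; it is an error in the written procedure and not merely missing detail.

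The consequence depends on which order staff used and on whether participants knew their group when they answered. Neither can be read from the documents, so confidence in actual harm is moderate. Under the stated assumptions, a baseline shift of 0.1 to 0.3 SD would raise a nominal 5% error rate to between 6.1% and 29.6% over correlations of 0.3 to 0.7, with bias possible in either direction.

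The reach is limited. The chi-square tests of adherence at Weeks 6, 9 and 13, recruitment and retention use no questionnaire baseline. Treatment satisfaction and credibility/expectancy (TSS and CEQ) are not collected at Baseline. Within-session MNWS and QSU changes do not use the Baseline visit. The CO, cotinine and pregnancy tests come before randomisation. What is exposed is the set of supporting mechanism comparisons.

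**What to change.** - Have all Baseline questionnaires completed in the Pre-Randomization arm before *Group Assignment* is opened, and remove from step 11 the wording that ties them to the assigned group.
- State which forms belong to the Pre-Randomization arm, and bring the Procedures, Random Assignment section and Measurement Occurrence Chart into line with the SAP.
- For participants already enrolled, establish from the REDCap record whether *Group Assignment* came before or after each Baseline form.
- Where step 11 was followed, keep those values but label them post-randomisation, and add a sensitivity analysis comparing follow-up values between arms without them.

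The cost is small: two steps reordered, one check of completion order and one extra analysis, with no added visits or procedures. If the Baseline forms sit in group-specific REDCap arms, they must be moved and the survey queue reset. The follow-up-only analysis loses precision only when the baseline/follow-up correlation exceeds 0.5.
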